### ***Control (RCT only)***

The control condition will involve screening and referral only. Patients will be provided with at least referrals to mental health treatment. If the participant desires, study staff will also facilitate a consult to the appropriate mental health service within VA for further assessment and treatment. Study staff will also provide a warm hand-off to the Women Veterans Coordinators and Domestic Violence Coordinators as needed/desired.

### ***Data Analysis***

**Overview of data analysis:** [name] will provide expertise with regard to statistical, research, and data management methods for the study. The sample size of the study allows good power to detect effects of approximately medium magnitude. Smaller effects may not reach significant, but can provide valuable data on likely effect size ranges for planning a larger scale trial. A small set of primary outcomes were selected with the goal of reducing Type I error and examining preliminary intervention effects. Data collected during the open pilot trial and initial randomized control trial will be analyzed separately. Preliminary analyses will include studies of patterns of missing data, dropout rates, and correlations among outcome measures. We will identify the appropriate distributional models for dependent variables. Continuous variables showing significant skew or kurtosis will be transformed. Using an-intent-to treat sample, comparisons between SHE and SR groups will be conducted using general linear models with a logistic regression model for our main outcome (number of risks). Using a general linear model we will also examine differences between the two conditions in terms of utilization of medical, psychological, and IPV-related services/resources at the two and four month follow-up period (secondary outcome).

**Data checking:** Participants' data will be directly exported from CIAS to a database that is under the VA firewall immediately after each participant session. All data will be screened for missing data, outliers ( $Z > 3.29$ ), and distribution abnormalities, with log transformation as needed. We will compare treatment groups on baseline characteristics (e.g., demographics). Analyses will adjust for baseline levels of dependent variables but will not test or adjust for any other baseline differences between conditions that result from randomization. Missing outcome data can create problems with the analysis and interpretation of intervention outcomes. We will conduct analyses to determine degree of attrition bias, and any variables shown to be associated with attrition will be included in the analytic models. Analyses will be based on all available data.

**Feasibility acceptability of intervention and study procedures (Open trial):** To assess the clarity, structure, content, and acceptability of the intervention we will assess the total intervention completion rate, retention rate, participant session ratings and total treatment acceptance scores gathered during the Open Trial. We will not have a comparison group for

participants in the open trial; however, we will examine rates of alcohol use, PTSD symptom severity, IPV occurrence and treatment/resource utilization at 2-months and 4-months post baseline. We will also examine women's immediate post-intervention ratings of the SHE intervention to explore the perceived utility of various program components (see appendix for exit interview questions).

**Study and treatment feasibility/acceptability (Aim 3):** Feasibility of the SHE intervention will be assessed by examining rates of session attendance, rates of treatment/assessment completion, rates of dropout, and reasons for termination. We will assess acceptability of the intervention via self-reported ease of use, helpfulness, and overall satisfaction using the SHE participants' responses from the Satisfaction with CIAS software scale and from the CSQ. We will examine means, modes, and median scores for these measures.

Feasibility of the research procedures will be assessed by examining study recruitment rates, refusal rates, follow-up rates and participants' willingness to be randomized. For follow-up retention rate (dichotomous), a chi-square analysis will be used. An urn randomization procedure will be utilized to avoid group differences at baseline. The success of random assignment in equating groups on baseline characteristics will be assessed. This will involve comparison of groups on demographic characteristics and number of risks. Should groups differ on any variables that show a relation to outcome, outcome analyses will be conducted both with and without adjusting for these covariates.

**Primary outcomes (Aim 4a):** Following the intention-to-treat principle, all women who completed the baseline assessment and who are randomized will be included in the analyses. Analyses will first test the hypothesis that SHE reduces the number of risks relative to control. Quantification of post-intervention behavioral change will be estimated by comparing the distributions of the number of risks in the two groups at baseline and follow-up. Within-person changes in the number of risks over time will also be examined. Specifically, women will be characterized by the number of risks (one through 3) at baseline. That will serve as a covariate in a model predicting number of risks at 2 and 4 months, which will be analyzed using generalized estimating equations (GEE) with a Poisson distribution specified. GEE is a method of repeated measures analysis commonly utilized for binary outcomes that allows for the inclusions of both categorical and continuous independent variables, as well as appropriate modeling of covariates when observations are correlated across time. The primary between group independent variable will be program group; dummy coded using the intervention as the reference category.

To further illustrate program effects, each of the participants will then be classified over the follow-up as 1) resolving all risks; 2) resolving some but not all risks; and 3) resolving no risks or increasing the number of risks. Intervention effectiveness will be measured by comparing the proportion of women resolving all risks, to the proportion of women resolving no risks or increasing risks between the groups. The proportion of women resolving all risks will also be compared to the proportion of women resolving some risks between groups.

**Secondary outcome (Aim 4b):** Analyses will also examine comparisons between groups in the extent of change in use of treatment (TSR and CPRS number of mental health visits) and resource utilization (EOR) (secondary outcome) as well as the extent of change on individual risk factors overtime using generalized estimating equations (GEE) (i.e., occurrence of IPV as measured by the CAS, screen positive for PTSD diagnosis as measured by the cut point of  $\geq 33$  on PCL-5, heavy drinking status as measured by the TLFB).

Analyses will also examine comparisons between groups in the extent of change in use of treatment (CPRS number of mental health visits and TSR) and resource utilization (EOR) as well as explore change in individual risk factors using (i.e., extent of alcohol use (AUDIT), severity of PTSD symptoms (PCL-5), frequency of IPV (CAS) using GEE. Outcomes of treatment and resource utilization, IPV, PTSD and alcohol use will be classified as continuous dependent variables. Scores from the outcome variables at follow-up will serve as the dependent variables. Intervention group will serve as the independent variable.

We will also calculate effect sizes for treatment efficacy for the aforementioned continuous study outcomes by examining the difference between the estimated adjusted means of the two groups at the end of the study divided by their standard deviation.

**Supplemental analyses:** In light of the challenges in promoting behavior change within treatment studies, we have included a limited number of assessments in order to promote analyses of the whether the intervention is associated with changes in the attitudes and beliefs that may serve as a mechanism of behavior change. Towards this goal, we will explore whether participants in SHE, relatively to control, vary in their attitudes towards seeking psychological care (ASPH), readiness to change drinking behavior (RCQ), and safety behaviors (SPBQ). These analyses will test whether SHE increases the mediators, whether the mediators are associated with the related behavioral outcomes, and whether there is a significant indirect effect of SHE through each mediator. We will use the products of coefficients method to test for significance of the indirect effects.

**Power Analysis:** Given the developmental nature of this study, our primary objective will be to determine a reasonable effect size for the SHE intervention for planning a future randomized trial, rather than to determine statistical significance between groups. Sample size requirements were estimated based on having adequate power to find clinically meaningful effects of the intervention on each of the primary outcomes, including reducing the percent of participants who screen positive for the health risk of PTSD, while also acknowledging the need to maintain a modest sample size in the initial test of a novel treatment approach. As documented below, we determined that an initial sample size of no more than 155 would meet these goals.

Research conducted by Himmelfarb and colleagues (2008) indicated that approximately 60% of VA women who screened positive for MST indicated PTSD. Given that we will identify women not only with MST, but a lifetime ST, we conservatively estimate that 60% of women included in the study will screen positive for PTSD. With an initial sample of no more than 155 women, retaining 126 over the 4-month follow-up, power would be .80 to detect an effect size  $h$  of .53 (equivalent to a medium effect size), with an alpha of .05, over the 4-month follow-up. This would be achieved, for example, with rates of PTSD at follow-up of 34% in the program vs. 60% in control.

The sample size of no more than 155 women would also be sufficient for detecting changes in the proportion of women indicating an alcohol use problem or occurrence of IPV over the follow-up. Based on findings suggesting that 7-14% of VA women with MST report SUD, and 64% of women with any lifetime sexual abuse report alcohol abuse, we conservatively estimate that 40% of women included in the study will screen positive for alcohol problems. Thus, the sample of no more than 155 accounting for attrition would allow a power of .80 to detect an effect size  $h$  of .44 of changes in alcohol use problems over the follow-up. This would be achieved with rates of alcohol use problems of 20% vs. 40% in control. Further, based on data indicating that 33% of women with a history of sexual victimization are revictimized, 44% of active duty military women report lifetime IPV, and studies indicating that IPV revictimization ranges from 18% to 74% over 6- to 9-month follow-ups (see Kuijpers et al., 2011), we conservatively estimate that 40% of women with a history of lifetime ST presenting at the VA would report lifetime IPV, and 25% would report a revictimization experience over the 4-month follow-up. A sample of no more than 155 accounting for attrition would allow a power of .80 to detect an effect size  $h$  of .46 in changes in IPV revictimization over the 4-month follow-up. This would be achieved with rates of IPV revictimization of 8.5% in the SHE program vs. 25% in the control group.

The sample size of no more than 155 will also be sufficient for detecting changes in the proportion of women who reduce the number of risks over the follow-up. Among the full sample of no more than 155 women, power would be .85 to detect an effect size  $h$  of .44 in any reduction (i.e., 1 to 0 risks, 2 to 1 risk, 3 to 2 risks, etc.) in the number of risks; which would be achieved, for example, with 20% of women in control and 40% of women in SHE reducing the number of risks reported over the follow-up. Power would also be adequate to examine reductions in the number of risks among women experiencing various numbers of risks (i.e., women reporting 1 risk vs. 2. vs. 3). In light of high comorbidity between PTSD, IPV, and

substance use, we projected that 50 women will report 1 risk, 50 women will report 2 risks, and 50 women will report three risks. Thus, among women reporting each number of risks (i.e., we expect 50 women will report 1 risk), power would be .73 to detect an effect size  $h$  of .64, which would be achieved with 20% of women in the control group reporting a reduction, and 50% of women in SHE reporting a reduction.

**Limitations** The limitations of this study include: potential issues related to disclosure of sensitive information, the use of self-report, assessment reactivity and effect on measured outcomes, the inclusion of only English-speaking participants, generalizability of study results to other Veteran or service member populations, and an inability to meaningfully examine ethnic/racial differences in the proposed sample.

**Revision:** Based upon experience during the Development and Trial Phase, evaluation of the program, and feedback from participants, the Investigator Team will revise the intervention. Information regarding the recruitment methods and retention of participants will be utilized in the design of a later clinical trial. This final revision phase will generate the final “product” of this treatment development study, to be used in the application to evaluate SHE in a large-scale clinical trial.

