### **The study aims are to:**

1. Develop our proposed preliminary computer-based intervention, incorporating information gained in informant interviews.
2. Perform a small open trial (n = 20) of SHE to assess feasibility of recruitment of target population and acceptability of intervention and study procedures.
3. Conduct an initial randomized control trial in a sample of no more than 155 women Veterans who screen positive for lifetime sexual trauma (ST) and have at least one risk factor (i.e., screen positive for intimate partner violence (IPV), posttraumatic stress

disorder (PTSD), and/or heavy drinking) to demonstrate the feasibility of SHE and the acceptability of SHE via participant report of ease of use, helpfulness, and overall satisfaction.

4. Examine preliminary evidence for the hypotheses that, relative to the control condition, screening and referral only (SR), SHE will result in:
  - Decreases in the number of risks (i.e., heavy drinking (4+ drinks on one occasion), screen positive for PTSD, screen positive for IPV) at the 2- and 4-month follow-up (*primary*).
  - Increases in resource and treatment utilization over the 2- and 4-month follow-up period (*secondary*).

The data will be used to demonstrate whether the effects of the intervention look promising to support a future large-scale randomized control trial and to suggest, in concert with results from clinical trials in related fields, the range of effect sizes that would be reasonable to expect in a future trial.

This is a multi-site study. At the Providence, RI based site (Women and Infants Hospital and Brown University), the specialized computer-based assessment and interactive intervention sessions will be developed and designed and staff members will also assist with data management. The Central Texas VA Healthcare System site will be the data collection site and the main site for participant recruiting, consenting, enrollment, intervention and follow-up. Staff at the two sites will work collaboratively throughout the project to supervise study staff, for reporting to the DOD and IRB's and in designing the assessment and intervention sessions, however, only the study staff at the Central Texas site will have access to participant PHI.

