For participants in the trial, we will also conduct a chart review using the VA Computerized Patient Records System to assess for mental health appointment attendance before and after the trial. This will entail documenting the number of mental health appointments attended at VA 4 months before the trial and 4 months after. The purpose of this information is to objectively document whether SHE increases engagement in VHA mental healthcare.

**Assessment of acceptability:** Satisfaction with CIAS Software Scale (SCSS) assesses participant satisfaction on items tapping on likeability, ease of use, level of interest, and respectfulness using a 1 – 5 Likert scale (1 = low, and 5 = high). This scale will be administered after every SHE module. The Client Satisfaction Questionnaire (CSQ) is an 8-item questionnaire which assesses the participant’s satisfaction with the intervention. The scale has good psychometric properties and correlates highly with other intervention measures. Only participants in SHE will complete these two measures immediately after the intervention.

**Measures of family and relationship functioning:** Prior research on Veterans has suggested that family and relationship functioning may influence treatment engagement, therefore we will include such measures as a covariate in analyses and to examine how family functioning may predict treatment completion, appointment attendance. The Quality of Marriage Index (QMI; Norton, 1983) will be used to assess relationship distress (6 items). The Family Assessment Device 12 (FAD; Epstein, Baldwin, Bishop) is a brief measure of general family functioning.

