**Table 1: Schedule of Assessment Measures**

Schedule of Assessments										
		Screening		Baseline		2-month		4-month		Measure Purpose
		SHE	Contro	SHE	Contro	SHE	Contro	SHE	Contro	
ST	SES-SFV+MST screener	X	X			X	X	X	X	Screening
	CSVQ	X	X							Screening
h c	GFM	X	X							Screening

	TLFB			X	X	X	X	X	X	Primary Outcome and Feedback
	RCQ			X	X	X	X	X	X	Attitude Change
	AUDIT			X	X	X	X	X	X	Exploratory Analyses
IPV	WAST	X	X							Screening
	CAS			X	X	X	X	X	X	Primary Outcome
	SPBC			X	X	X	X	X	X	Attitude Change
PTSD	THS			X	X	X	X	X	X	Primary Outcome
	PCL-5	X	X			X	X	X	X	Primary Outcome and Screening
Tx Use	EOR			X	X	X	X	X	X	Primary Outcome
	TSR			X	X	X	X	X	X	Primary Outcome
	ASPH			X	X	X	X	X	X	Attitude Change
Acceptability	SCSS			X						Treatment Acceptability
	CSQ-8			X						Treatment Acceptability
Relationship Function	QMI/ FAD-12			X	X	X	X	X	X	Secondary outcomes/covariate

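### The number of risks is assigned both a logistic regression and a Poisson GEE; the baseline-adjustment rules conflict, Table 1 labels three further measures primary, and the five stated powers share no single test convention

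*Combined protocol and SAP*

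**What the plan says.** **Model.** Section 4, Data Analysis, overview paragraph, plans comparisons by "general linear models with a logistic regression model for our main outcome (number of risks". The Aim 4a paragraph takes the number of risks at 2 and 4 months, with the baseline number as covariate, "which will be analyzed using generalized estimating equations (GEE) with a Poisson distribution specified". SHE is the reference category.

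**Baseline adjustment.** The data-checking paragraph adjusts for the baseline level of the outcome but "will not test or adjust for any other baseline differences between conditions that result from randomization". The Aim 3 paragraph compares the groups on demographics and number of risks, and adds: "Should groups differ on any variables that show a relation to outcome, outcome analyses will be conducted both with and without adjusting for these covariates". Separately, the data-checking paragraph says that "any variables shown to be associated with attrition will be included in the analytic models".

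**Labels.** The study aims in Section 1 and the Trial Aims in Section 3 define the primary outcome as a count of heavy drinking, a positive PTSD screen and a positive IPV screen. The Section 1 aims list "Increases in resource and treatment utilization over the 2- and 4-month follow-up period" as secondary; the Trial Aims, the overview and Aim 4b agree. Table 1 nevertheless marks EOR, TSR and THS "Primary Outcome". The Power Analysis treats the PTSD screen as one of several primary outcomes, while Aim 4b analyses each risk separately under the secondary heading.

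**Power.** Alpha is .05 with no side given. The Power Analysis states .80 for PTSD (126 retained of 155), .80 for alcohol and .80 for IPV (both after attrition), .85 for any reduction in the number of risks (full 155), and .73 within a group of 50 women sharing the same number of risks. It calls power across those groups adequate.

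**The concern.** The Power Analysis puts a reasonable effect size for a later trial ahead of significance. That number should come from one named model, on one scale, with a known rule for covariates. As written, an analyst could report an odds ratio or a rate ratio, with or without imbalance-triggered covariates, and cite the plan for each. The labels matter because the overview says a small set of primary outcomes was chosen to limit Type I error, and the reader cannot tell from Table 1 what that set is. The power figures matter less given the estimation aim, but they support the sample size, and a reader cannot tell which test they describe.

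**Working it through.** **Models side by side.** Both paragraphs are current text and name the same outcome. Logistic regression needs a binary or ordered-category version of a 0 to 3 count, and the overview defines neither. The Poisson GEE models the count directly over two visits. The follow-up distribution of the count is not given, so the numerical gap between the two effect measures cannot be computed.

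**Adjustment rules side by side.** One paragraph excludes adjustment for baseline differences other than the outcome's own baseline. The other makes such adjustment conditional on an observed imbalance in a variable related to outcome. Both cannot be followed when an imbalance occurs, and neither result is named as primary.

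**Power.** Inputs are from the Power Analysis. Equal arms are taken from the statement in the benefits section that half of participants receive no intervention.

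Effect size: h = |2·arcsin√p1 − 2·arcsin√p2|. The example rates reproduce the stated values:
- PTSD .60 vs .34: .527 (stated .53)
- Alcohol, and any reduction, .40 vs .20: .442 (stated .44)
- IPV .25 vs .085: .456 (stated .46)
- Per risk group .50 vs .20: .644 (stated .64)

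Power = Φ(h·√(N/4) − z), with z = 1.645 one-sided or 1.960 two-sided. Example, any reduction at N = 155: .44 × √38.75 = 2.739. One-sided Φ(1.094) = .863; two-sided Φ(0.779) = .782.

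| Outcome (stated h) | N | Stated | One-sided | Two-sided |
|---|---|---|---|---|
| PTSD (.53) | 126 | .80 | .908 | .845 |
| Alcohol (.44) | 126 | .80 | .795 | .695 |
| IPV (.46) | 126 | .80 | .826 | .733 |
| Any reduction (.44) | 155 | .85 | .863 | .782 |
| Any reduction (.44) | 126 | not given | .795 | .695 |
| Per risk group (.64) | 50 | .73 | .732 | .619 |
| Per risk group (.64) | 41 | not given | .657 | .536 |

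The 41 is 50 × 126/155 = 40.6, rounded up.

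**Cross-check with the pooled z test, one-sided.** Power = Φ[(|p1 − p2|·√n − z·√(2·p̄·q̄)) / √(p1·q1 + p2·q2)], n per arm. For IPV with n = 63: (.165 × 7.937 − 1.645 × .528)/.515 = .856, so power is .804. The same formula gives alcohol .795, any reduction .864 at 155 (.854 at 150, the sum of three groups of 50), per risk group .729, and PTSD .907 (.841 two-sided).

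One-sided .05 therefore fits four of the five figures and fails only for PTSD. A two-sided continuity-corrected test comes close for PTSD (.792) but gives .619 for alcohol, .614 for IPV, .724 for any reduction at 155 and .486 per risk group. No convention tried fits all five.

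**The case against.** **The logistic clause may be loose summary wording.** Aim 4a is the dedicated, detailed paragraph. The overview might mean an ordinal model, or the later classification of women as resolving all, some or none of their risks. That makes it clear which text to keep, but the clause names the number of risks as the main outcome and still stands.

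**The balance check may be descriptive, and with-and-without reporting is already a sensitivity pair.** Fair, but the other paragraph rules out the adjusted half, and the plan does not rank the two results.

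**THS helps classify PTSD by DSM criteria, which might explain its label.** Aim 4b defines the PTSD risk by the PCL-5 cut point alone, so THS is not part of the primary count.

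**On power,** the hypotheses are directional, so one-sided testing may have been meant. The .85 is openly given for the full sample. The GEE uses all available data, so women seen only at 2 months contribute and 126 is a lower bound. All of this stands; what remains is that the side is unstated and the bases are mixed.

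**Stronger readings the documents do not support:**
- That every power is inflated. The PTSD figure is too low, and the documents do not establish that tests must be two-sided.
- That the family and relationship measures enter the primary model because "we will include such measures as a covariate in analyses". That sentence is about treatment engagement and completion, and Aim 4a names only the baseline number of risks.
- That the attrition-variable rule breaks the no-adjustment rule. It concerns predictors of dropout, not differences between arms. With 155 − 126 = 29 women expected lost, it is the stated protection against attrition bias.
- That the Poisson standard errors will be wrong. The plan does not specify model-based errors, and the correlation among the risks is not given.

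**Conclusion.** The concern holds and should be fixed before analysis. Two contradictions bear on the trial's main product: two models with different effect measures for one primary outcome, and two incompatible rules for chance baseline imbalance with no primary result named. The labelling conflict is clear but smaller: EOR, TSR and THS are marked primary against the aims, and the individual risks are called primary in one place and analysed as secondary in another, although the aims plainly make them components of the primary count.

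The power problem is one of disclosure. One-sided .05 accounts for alcohol (.80), IPV (.80 to .83), any reduction (.85 to .86) and per risk group (.73). The PTSD figure is understated. With attrition at the planned rate, any reduction falls to .80 one-sided or .70 two-sided, and per risk group to .66 or .54; the last two do not support calling that power adequate. All five powers are for yes/no outcomes and say nothing directly about the Poisson GEE. These figures assume equal arms, normal-approximation tests and, for the groups of 50, the same proportional loss as overall.

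**What to change.** - **Overview:** delete the logistic clause and refer to Aim 4a.
- **Aim 4a:** name the Poisson GEE with baseline number of risks as the primary analysis. Report the rate ratio with 95% CI and robust standard errors, and state its direction: with SHE as reference, a ratio above 1 means more risks in control.
- **Data checking and Aim 3:** keep one baseline rule. The model adjusted for baseline number of risks is primary; the imbalance-triggered model is a sensitivity analysis. Leave the attrition-variable rule as planned, and report results with and without those variables.
- **Table 1:** relabel EOR and TSR as secondary and remove the primary label from THS.
- **Power Analysis, roles:** describe the individual risks as components of the primary count, analysed separately as secondary.
- **Power Analysis, figures:** state the side and put every figure on it, with attrition shown. Two-sided .05: PTSD .85, alcohol .70 and IPV .73 at 126; any reduction .78 at 155 and .70 at 126; per risk group .62 at 50 and .54 at about 41. If one-sided .05 is intended, in the same order: .91, .80, .83; .86 and .80; .73 and .66. Say that these refer to binary outcomes, and drop the claim of adequacy for the per-risk-group power.

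**Cost:** no new data, visits or participants. Most changes are wording; ranking the imbalance-triggered model as a sensitivity analysis is a choice the plan has so far left open. Several stated powers become less favourable, while PTSD's rises.

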### ***Randomization (RCT only)***

The computer program will randomly assign participants to condition and the research assistant will remain blinded.

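### The urn factors are not named, no outcome model is committed to including them, and the two adjustment rules in Data Analysis conflict

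*Combined protocol and SAP*

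**What the plan says.** **Allocation.** The Randomization (RCT only) subsection of Section 4 says only: "The computer program will randomly assign participants to condition and the research assistant will remain blinded". The method appears later, in the Aim 3 feasibility paragraphs of Data Analysis: "An urn randomization procedure will be utilized to avoid group differences at baseline". Neither place gives the urn factors, their levels or the urn parameters. The Aim 3 text then describes a check of the result: "This will involve comparison of groups on demographic characteristics and number of risks". That is a comparison after allocation; it is not stated to be the list of urn inputs.

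**Adjustment.** Four statements bear on which covariates enter.
- Data checking: "Analyses will adjust for baseline levels of dependent variables but will not test or adjust for any other baseline differences", meaning differences produced by randomization.
- Two sentences later: "any variables shown to be associated with attrition will be included in the analytic models".
- Aim 3: where the arms differ on a variable related to outcome, "outcome analyses will be conducted both with and without adjusting for these covariates".
- Measures (family and relationship functioning) and Table 1: QMI and FAD-12 are intended as covariates.

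**Models.** Aim 4a fits a Poisson GEE to number of risks at 2 and 4 months, with baseline number of risks as a covariate. The comparison of women who resolve all, some or none of their risks lists no covariate. The secondary analyses of continuous outcomes name only intervention group as the independent variable, and the supplemental attitude analyses list no covariates.

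**The concern.** An urn that balances prognostic baseline variables removes part of the chance variation between the arms. If the analysis leaves those variables out, its standard error still counts that variation as random error. The standard error is then too large and the test conservative. The remedy is to analyse by the factors used to randomize, and the plan does not say it will. The one rule that reacts to baseline variables generally, in the Aim 3 text, depends on an observed imbalance, which is what the urn is there to prevent.

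At stake is precision. The Power Analysis section says that the main purpose is to obtain an effect size for planning a later trial, so interval width is a main product of this study. There is also a plain ambiguity: one paragraph says baseline differences will be neither tested nor adjusted for, and the other says they will be tested and, in some cases, adjusted for.

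**Working it through.** **1. The plan's nearest figure.** The plan states no standard error and claims no gain from balancing. The closest figure is power of .85 for 20% versus 40% of women reducing their number of risks, with all 155 women. With h = 2·asin(√.40) − 2·asin(√.20) = .442 and power = Φ(h·√(n/2) − z), n = 77.5 per arm gives .866 one-sided and .786 two-sided at alpha .05. The stated value is therefore matched only by a one-sided test. No covariate gain is built into it.

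**2. Which models would contain an urn factor as the plan stands.**

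| Model | Number of risks, if an urn factor | Any other urn factor |
|---|---|---|
| Primary GEE, number of risks | Yes | Not committed |
| Resolved all / some / none | Not committed | Not committed |
| Utilization (TSR, CPRS visits, EOR) | Not committed | Not committed |
| Attitudes (ASPH, RCQ, safety behaviors) | Not committed | Not committed |

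The attrition rule brings in an urn factor only if it happens to predict dropout. The Aim 3 rule does so only if the factor is visibly imbalanced. The QMI/FAD-12 provision does so only if one of those scales is an urn factor. In the resolved all/some/none comparison, baseline number of risks determines which categories are possible: a woman with one risk cannot resolve only some.

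**3. Size for one omitted factor.** Let R² be the share of outcome variance that the factor explains beyond the baseline outcome. The documents give no value, so a range is assumed. With close balance:
- standard error ratio = 1/√(1 − R²)
- actual two-sided type I error = 2·[1 − Φ(1.96/√(1 − R²))]
- power at 63 per arm (126 retained) with d = .442·√(63/2) = 2.48: omitted, Φ((d − 1.96)/√(1 − R²)); included, Φ(d/√(1 − R²) − 1.96)

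| R² (assumed) | SE ratio | Type I error | Power, omitted | Power, included |
|---|---|---|---|---|
| .01 | 1.005 | .049 | .700 | .703 |
| .05 | 1.026 | .044 | .703 | .721 |
| .10 | 1.054 | .039 | .708 | .744 |

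**4. Simulation with a real urn.** I ran 4,000 null trials per scenario, each with 126 women. Assumptions: baseline risks spread evenly over 1 to 3, one binary prognostic covariate, two visits with persistent individual differences, no missing data, Poisson GEE with independence working correlation and robust standard errors. The ratio is mean robust standard error over empirical SD of the estimate.

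| Urn on | In the model | Ratio | Type I error |
|---|---|---|---|
| Risks | Risks | 0.99 | .047 |
| Covariate | Risks | 1.03 | .041 |
| Risks and covariate | Risks | 1.04 | .043 |
| Risks and covariate | Both | 0.99 | .049 |
| Risks | Neither | 1.16 | .021 |

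The last row shows what omitting a strong urn factor can do. It is not the planned primary model, and it is not an estimate for the secondary models.

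**5. Why the formula is an upper limit.** Under simple randomization in the same simulation, adding the covariate to a model with risks cut the empirical SD from .0877 to .0823. That implies R² of about 1 − (.0823/.0877)² = .12, for which the formula gives an excess of .0877/.0823 − 1 = 6.6%. The urn scenarios that omitted the covariate showed about 3% to 4%, because the urn balances only partly.

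**The case against.** The strongest reply is that there may be no error to correct. No urn factor is named, so no one can show that a particular factor is missing from a particular model. The only non-demographic variable in the planned balance check is number of risks, and the primary GEE already adjusts for it; in that case the simulated standard error is right (ratio 0.99). Any error is conservative, so it adds no false positives. The stated power figures take no credit for balancing, so none is invalidated. All of this stands, and it limits the point to a modest one.

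A reader might infer that the plan bars every covariate except the baseline outcome. The documents do not support that: attrition predictors, the family and relationship measures, and imbalanced variables related to outcome can all enter. The data-checking rule also concerns differences that arise from randomization and does not mention design factors.

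The reply does not show that the urn factors will be in the models. Each of those routes depends on something other than their having been used to randomize. That the factors are unnamed is itself a gap.

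**Conclusion.** The point holds as one of specification, with a modest and conservative effect on precision. The urn factors are unnamed, no model is committed to including them, and the data-checking and Aim 3 rules contradict each other.

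If number of risks is the only factor, the primary analysis is unaffected and the point concerns only the utilization, attitude and resolved all/some/none analyses. For any other prognostic factor left out, standard errors are at most 0.5%, 2.6% or 5.4% too large for residual R² of .01, .05 or .10. In the simulations with the planned covariate kept, the excess was about 3% to 4%, with type I error of .041 to .043.

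Two stronger conclusions are tempting and not supported. One is that the primary standard errors are too large; that depends on unnamed factors and is false if number of risks is the only one. The other is that the loss is large, as it would be with R² of 20% or 30%. The relevant R² is what remains after the baseline outcome, and nothing in the documents supports values that high.

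These figures assume 1:1 allocation and two-sided tests at .05. The simulation also assumes robust standard errors; the plan does not say which kind it will use.

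**What to change.** 1. In the Randomization subsection and the Aim 3 text, name the urn factors and their levels before the first randomization (for example clinic, Waco or Temple, and baseline number of risks, if those are what the program uses).
2. Enter those same factors as covariates in every between-arm model: primary, secondary, attitude, and resolved all/some/none. Do this whether or not the arms look balanced, and alongside the baseline level of the outcome.
3. Replace the data-checking rule on baseline differences and the Aim 3 with-and-without rule by this single prespecified rule. The attrition and family-functioning provisions serve other purposes and need not change for this point.

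The cost is a few sentences and one to three extra model terms, on data already collected.
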